3 METHODOLOGY

3.1 Summary of Study Design

This study will be designed as an observational, population-based, cross-sectional study. A total of 2700 postmenopausal women over age of 50 inclusive and physically living in a community will be included in the study. As suggested by Chinese local guideline, postmenopausal women are eligible for a subsidized screening program (blood chemistry, radiology and/or DXA assessment) for osteoporosis clinical management. A cluster sampling (two-stage random sampling) by age and geographic region will be performed to represent a geographically generalized Chinese population with specific gender and age groups relevant to postmenopausal osteoporosis and VF prevalence. Subject recruitment will be based on various local demographic records including Government resident lists, local population lists, electoral registers, and health registers by a study invitation and a referral to the investigators at each study center. By 1 onsite visit, an interview, DXA measurement, and thoracic/lumbar spine X-ray will be performed to collect a set of data regarding socioeconomic/medical (interview-based questionnaire), VF assessment (radiographs), and specific densitometric information (BMD DXA) from the participant. No follow-up visit is required for this cross-sectional study unless a spine imaging and/or BMD measurement cannot be made during the visit due to a particular reason in the study or from the subject. The recruitment period is estimated between 6 and 9 months and initiated at any time point during a calendar year, because a seasonal or social impact on the data of interest is minimal. Analyses will be based on epidemiological data and then be expanded to establish a vertebral fracture risk assessment model.

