3.2 Study Population

This study will include approximately 2700 community-dwelling postmenopausal women aged 50 or above at 8 - 10 participating sites throughout China. A two-stage cluster sampling will be performed for the study. Firstly, geographic regions are divided into 'clusters' and then a randomized stratified sampling will be performed by age group using a computerized random selection on various demographic records (as indicated in Section 3.1) from the participating sites and the communities by which they cover. All subjects are expected to have an interview for questionnaire, vertebral imaging and BMD measurement. To be eligible for the study, participants must fulfill the following inclusion and exclusion criteria (Section 3.3 and 3.4):

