8.1 Statistical Methods

This section outlines the statistical analysis strategy and procedures for the study. If, after the study has begun, changes are made to primary and/or key secondary hypotheses, or the statistical methods related to those hypotheses, then the protocol will be amended. Changes to exploratory or other non-confirmatory analyses made after the protocol has been finalized, along with an explanation as to when and why they occurred, will be listed in the CSR for the study. Post hoc exploratory analyses will be clearly identified in the CSR. A separate SAP will be created for this study.

8.1.1 Primary Objective(s): Calculation of Epidemiological Measure(s) of Interest (e.g. descriptive statistics, hazard ratios, incidence rates, test/retest reliability)

The study's primary objective is to investigate the prevalence of radiographic vertebral fractures in community-dwelling postmenopausal women in China. Descriptive statistics will be made to statistically address this objective. No hypothesis testing will be applied in the study for this primary objective.

Point estimates (percentage) of prevalence by overall study population and by age group and/or geographic region will be calculated and displayed. A fracture case is defined and counted as the subject with the presence of at least one vertebra classified as grade 1, 2, or 3 semi-quantitatively by Genant's score as agreed by both study radiologists.

Point estimates of prevalence rates by overall and geographic region will be adjusted by a nationwide age distribution using the database from Basic Statistics on National Population Census 2010, National Bureau of Statistics of China [53]. A direct method of adjusting rates will be made to give age-standardized prevalence. Age-standardized rate by regional age distribution data may be calculated subject to site location and will be specified in the SAP before database lock and study analyses.

A corresponding two-sided 95% confidence interval (CI) for each individual point estimate will be given. This 95% CI is based on a direct calculation of the exact binomial distribution. A more conservative method, the Wilson Score CI [52], will be applied to give 95% CIs for all point estimates and compared with the exact binomial distribution.

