To test reproducibility for fracture adjudication, intra- and inter-observer reliabilities will be tested using a sample of first 100 X-ray films from any participating site in the study. Intra-observer and inter-observer agreement will be calculated by kappa statistic. A κ is 0.81 or above suggests very good agreement.

The statistical analyses for primary objective are summarized in Table 8.1.1.1.

Table 8.1.1.1 Statistical Analysis Approaches on Primary Objective

VF Prevalence	Rate	Estimate*
Overall	Crude/Age-Standardized Rate	Point and 95% CI
Age Group§	Crude Rate	Point and 95% CI
Region^	Crude/Age-Standardized Rate	Point and 95% CI
Age Group and Region△	Crude Rate	Point and 95% CI
Genant's Grade※	Crude Rate	Point and 95% CI

* Based on exact binomial distribution 95% CI and Wilson Score 95% CI;
§ Age group will be given by 50 – 54, 55 – 59, 60 – 65, 65 – 69, 70 – 74, 75 – 79, and 80+; and by < 65 and ≥ 65;
^ Participating sites will be grouped by 5 regions in China: North, South, Southeast, Southwest, and Central;
△ Prevalence rate will be presented by all age groups and overall in individual regions in China;
※ Genant's Grade by 1, 2 or 3.

8.1.2 Secondary Objective(s): Calculation of Epidemiological Measure(s) of Interest (e.g. hazard ratios, incidence rates, test/retest reliability)

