8.1.2.1 Prevalence of Osteoporosis

In the study, prevalence of osteoporosis in community-dwelling postmenopausal women in China will be investigated as a secondary objective. Descriptive statistics will be made to statistically address this objective. Point estimates (percentage) and corresponding 95% CI (exact binomial and Wilson score) will be presented for each analysis category and will be adjusted by age distribution in China [53]. Prevalence rates will also be given by age group and geographic region. A case with osteoporosis is counted based on the definition in Section 4.

The prevalence of osteoporosis will be presented as overall and by different diagnostic criteria and will be listed separately to allow an evaluation on the frequency distribution of each individual diagnostic setting in the study population.

The analysis of osteoporosis prevalence is displayed in the Table 8.1.2.1.

Table 8.1.2.1 Statistical Analysis Approaches on the Prevalence of Osteoporosis

Osteoporosis	Rate*	Estimate**	Frequency ***
Overall	Crude/Age-Standardized	Point and 95% CI	Percent
By DXA BMD [^]	Crude/Age-Standardized	Point and 95% CI	Percent
By Fragility Fracture [△]	Crude/Age-Standardized	Point and 95% CI	Percent & Cumulative

* Prevalence rates will be sub-analyzed by age group (50 – 54, 55 – 59, 60 – 65, 65 – 69, 70 – 74, 75 – 79, and 80+; and by < 65 and ≥ 65) and/or geographic region (North, South, Southeast, Southwest, and Central);
 ** Based on exact binomial distribution 95% CI and Wilson Score 95% CI;
 *** Calculation of frequency is relative to overall percent (100%);
 ^ the subject with a T-score ≤ -2.5 as suggested by a DXA measurement
 △ The subject with DXA measurement with a proven non-pathological major fracture as reported by the medical history or as suggested by radiology.

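### The planned prevalence intervals contain no between-site variance, so they may be too narrow when read as precision for women in China.

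*Combined protocol and SAP*

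**What the plan says.** The primary objective is descriptive, with no hypothesis test. Section 8.1.1 gives each point estimate a two-sided 95% interval: "This 95% CI is based on a direct calculation of the exact binomial distribution". It then adds: "A more conservative method, the Wilson Score CI [52], will be applied to give 95% CIs for all point estimates". Overall and regional rates are also standardised to the 2010 census age distribution: "A direct method of adjusting rates will be made to give age-standardized prevalence". The footnote to Table 8.1.1.1 attaches the same two methods to every row, crude and age-standardised: "Based on exact binomial distribution 95% CI and Wilson Score 95% CI". Section 8.1.2.1 repeats this for osteoporosis: "Point estimates (percentage) and corresponding 95% CI (exact binomial and Wilson score) will be presented for each analysis category".

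On design, section 3.1 states: "A cluster sampling (two-stage random sampling) by age and geographic region will be performed to represent a geographically generalized Chinese population". Section 3.2 plans "approximately 2700 community-dwelling postmenopausal women aged 50 or above at 8 - 10 participating sites throughout China". Section 6.1.1.1 calls the five regions the first-stage clusters and has an age-stratified random list drawn separately at each site. The table footnote adds: "Participating sites will be grouped by 5 regions in China: North, South, Southeast, Southwest, and Central".

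No section gives an ICC, design effect, site term, survey-type variance, or variance for a directly standardised rate. Section 8.1 announces a separate SAP; on this topic it expressly defers only the use of regional age distributions.

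**The concern.** All five named regions are included, so they contribute no sampling variance of their own: they are strata. The sites within them are the clusters. Exact binomial and Wilson intervals both assume independent women, so neither allows for a difference between sites, and setting one beside the other is no safeguard.

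Because the primary result is an estimate with its interval, the interval is the study's statement of precision. If sites differ, a reader who takes it as precision for China is told that the study is more precise than it is. Osteoporosis may be more exposed than fracture: section 6.1.2.2 has each site use one DXA machine or one make, so a residual machine shift would move all women at a site together.

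Two smaller points arise in the same text. A directly standardised rate is a weighted sum of seven age-specific proportions, not one count over one denominator, and the plan does not say how a binomial formula is to be applied to it. Wilson is also described as the more cautious interval, which it is not here.

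**Working it through.** **1. The plan's own figures.** The age-group sizes in Table 8.3.1 (44, 81, 100, 90, 80, 70, 53) sum to 518. Then 518/0.95 = 545 per region, and 5 × 545 = 2725, stated as about 2700. The sample size therefore reproduces with no design effect.

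**2. The planned interval.** Evaluable women: 5 × 518 = 2590. Multiplying the Table 8.3.1 prevalences (5, 7, 12, 16, 20, 23, 37%) by the group sizes gives 85.98/518 = 16.6%. The exact interval is 15.18–18.09% (half-width 1.45 points); Wilson is 15.22–18.08%, slightly narrower. The binomial SE is √(0.166 × 0.834/2590) = 0.731 points. Fixing the age quotas multiplies the variance by 0.942, so with no site differences the interval is slightly conservative.

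**3. Adding sites.** The variance factor is about 0.942 + (m − 1) × ICC, where m is the effective number of women per site.
- 10 sites (assumed two per region): m = 259.
- 8 sites (assumed three regions with two sites, two with one): m = (6 × 259² + 2 × 518²)/2590 = 362.6.

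The factor exceeds 1 once the ICC passes about (1 − 0.942)/258 = 0.0002 with 10 sites. At ICC 0.0025 with 10 sites it is 0.942 + 258 × 0.0025 = 1.587. The true SE is then 0.731 × √1.587 = 0.921, and 1.452/0.921 = 1.58 SEs corresponds to about 88–89% coverage.

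**4. Simulation.** There were 20,000 runs per cell, with a normal site effect on the logit scale, Table 8.3.1 inputs and equally weighted regions. Repeat runs agree within about 1 point. Coverage of the nominal 95% exact interval for the crude overall rate:

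| Assumed ICC | Between-site SD (points) | 10 sites | 8 sites |
|---|---|---|---|
| 0 | 0 | 96% | 96% |
| 0.0005 | 0.8 | 95% | 94% |
| 0.001 | 1.2 | 93% | 92% |
| 0.0025 | 1.9 | 89% | 87% |
| 0.005 | 2.6 | 83% | 79% |
| 0.01 | 3.7 | 73% | 66% |

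Read as conditional on the participating sites, the same interval covers 96% at every ICC.

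**5. Regional crude rates (518 women).** The exact interval is 13.5–20.1%. At ICC 0.0025, coverage is 90% if the region has two sites and 83% if it has one; at 0.01, 73% and 60%.

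**6. Age-standardised overall rate.** The census weights are not in the documents, so three sets were assumed for ages 50–54 to 80+: 24/23/18/12/10/7/6%, 20/19/17/14/12/9/9%, and equal weights. They give 12.7%, 14.4% and 17.1%.
- Without clustering, the SE of the weighted sum, √Σw²p(1 − p)/n, is 0.95–1.00 times the binomial SE at the standardised proportion. Wilson evaluated at that proportion covers 95–96%.
- With clustering, Wilson coverage for 10/8 sites is 88–90% / 86–88% at ICC 0.0025 and 72–76% / 66–70% at 0.01.

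**7. Osteoporosis.** Take the 27.3% prevalence quoted in section 1.1 and, as a simplification, one threshold on one normal variable: ICC = s² × 0.332²/(0.273 × 0.727). An assumed between-site machine SD s of 0.03 to 0.10 of the between-woman SD gives an ICC of 0.0005 to 0.0056.

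**The case against.** The strongest objection is that the loss rests wholly on assumed ICCs. For fracture, the documents point to a small value: section 1.2 describes vertebral deformity as fairly uniform across world regions, and section 4 has films read by blinded radiologists under one protocol. For osteoporosis, the two-step cross-calibration in section 4 should reduce machine shifts. The printed between-brand equations cover lumbar spine and femoral neck but not total hip, which can also define a case. All of this stands as an argument about size. It does not put a between-site term into the interval.

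Second, no section says that sites are drawn at random. Widening an interval does not by itself justify inference from chosen sites to China, and for the participating sites the exact interval is adequate. This also stands, which is why a plain conditional label is an acceptable remedy.

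Third, the crude rate reflects the age quotas, so the nationally referenced figure is the standardised one. That is correct, but step 6 shows a similar loss there.

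Three stronger readings are tempting and not supported:
- That the intervals are known to be too narrow. At ICC 0 they cover 96%; the error appears only once sites differ.
- That the standardised rates will get badly misplaced intervals. That would require placing the crude interval around the standardised rate, which no section proposes.
- That every regional row rests on one or two sites. Between 8 and 10 sites in five regions average 1.6 to 2, but the allocation is not stated.

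**Conclusion.** The concern holds conditionally and is worth fixing. It is certain that the stated intervals omit between-site variance while the stated target is women in China. If sites within regions differ more than trivially, the intervals are too narrow for that target. How much too narrow cannot be known from the documents: the loss is negligible at an ICC of 0.0005 and large at 0.01, under the assumed site layouts and Table 8.3.1 prevalences. Point estimates are unaffected. National age-group rates, on which the sample size was built, are little affected: the SE is understated by a factor of 1.03 to 1.08 at ICC 0.0025. The undefined variance for standardised rates and the description of Wilson are minor; without clustering, the numerical effect of either is small.

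**What to change.** Amend sections 8.1.1 and 8.1.2.1, with formulas in the separate SAP, before database lock.

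**(a) Overall crude and age-standardised rates.** Pre-state one option.
- (i) Use a site-clustered variance with region as stratum and a t quantile on sites minus regions degrees of freedom (about 3–5). Include a rule for any single-site region, for example the pooled within-region between-site variance from the other regions. Describe the interval as model-based, since sites are not stated to be randomly drawn. In simulation over ICC 0 to 0.01, this covered 94.8–95.1% with 10 sites and, with the pooled rule, 95.3–96.9% with 8.
- (ii) Keep the binomial interval and state that it is conditional on the participating sites and does not measure precision for China.

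Under either option, label regional intervals as conditional on their sites.

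**(b) Minor.** For age-standardised rates, compute the interval from Σw²p(1 − p)/n on the logit scale, or from the site-clustered variance of the same weighted sum under (a)(i).

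**(c) Minor.** Delete the description of Wilson as the more conservative method.

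**Cost.** No new data. Option (i) widens the crude overall half-width from about 1.45 points to about 1.7 (10 sites) or 2.5 (8 sites) even if sites do not differ. Option (ii) costs no width but gives up the claim of precision for China.

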In the study, vertebral fracture is defined as the presence of at least one vertebra morphometrically classified as grade 1, 2, or 3 on Genant's score as agreed by the both radiographic assessments in the study. Two (2) experienced radiologists who are blinded to the study will separately review the vertebral morphology and grade Genant's Score as per protocol. Radiologists will receive additional training to reduce variability between inter-observer interpretations. Prior to the study, each site will forward sample radiographs to the radiology coordination site for quality assessment and to check compliance with the protocol and technical standard. Intra- and inter-observer reliabilities will be tested using first 100 X-ray images from any study site before the adjudication starts. If there is a disagreement in terms of Genant's grading between two study radiologists, a third party radiological review will give a final decision.

The Genant semi-quantitative approach has been established a reliable and reproducible assessment in radiographic vertebral fracture. The intra-observer agreement for prevalent vertebral fracture was generally between 93 and 97% ($\kappa = 0.73 - 0.89$) [51], regardless of the radiologist's experience. As compared with reviewer's experience and other quantitative methods, an inter-observer agreement by difference in experience and method was between 92 and 94% ($\kappa = 0.65 - 0.74$) [51].

Definitions of Osteoporosis

In the study, osteoporosis is defined [3, 41] if the subject has at least one of the following as:

- A BMD T-score ≤ -2.5 in at least one of the anatomic sites including the lumbar spine, the femoral neck, and the total hip;
- A proven prior non-pathological fragility fracture.

A fragility fracture is defined as a fracture that occurred with minimal trauma at a typical site of osteoporotic fracture that would be unlikely to cause fracture in a non-osteoporotic adult. This assessment will be made based on self-reported fracture section included in the questionnaire and a review of medical history/documents/physical examination, or as suggested by the radiographic imaging in the study.

5 Study Flow Chart

Study Period:	Enrollment		Observation	Follow-Up
Visit Number/ Title:	Invitation#	Screening [△]	Study Visit**	Unscheduled Visit***
Study Day	NA	1	1	NA
Informed Consent		X		
Medical History [※]		X		
Inclusion/Exclusion Criteria		X		
Investigator-administered Questionnaire [¶]		X	X	
Physical Examination*				

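### Agreement between the two study radiologists is planned only on the first 100 films; kappa from all double-read women would be far more precise, cover every site and need no extra reads

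*Combined protocol and SAP*

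**What the plan says.** Section 4 (Vertebral Radiology) tests intra- and inter-observer reliability "using first 100 X-ray images from any study site before the adjudication starts". Section 6.1.2.3 repeats the sample and places the test ahead of interpretation of the results. Section 8.1.1 makes it the reproducibility test for the adjudication, "using a sample of first 100 X-ray films from any participating site". It adds: "Intra-observer and inter-observer agreement will be calculated by kappa statistic", and a value of "0.81 or above suggests very good agreement". No confidence interval for kappa is stated, and no action depends on the value.

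Separately, Section 4 provides that two "experienced radiologists who are blinded to the study will separately review the vertebral morphology and grade Genant's Score". Under Section 8.1.1 a woman is a case when she has at least one vertebra of grade 1, 2 or 3, classified "semi-quantitatively by Genant's score as agreed by both study radiologists". Where the two grades differ, "a third party radiological review will give a final decision".

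The only other kappa in the plan (Section 8.1.3) compares the onsite reading with the blinded reading, which is a different question. The supplied text plans no agreement statistic between the two study radiologists over the full set of reads.

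**The concern.** The primary endpoint is a graded visual reading, so anyone using the prevalence figures will want to know how reproducible that reading was. The plan's answer would come from 100 films. With fracture prevalence well below one half, kappa from so few films depends on a small number of positive readings and carries a wide margin. Taking the first films from any site also does not require that all 8 to 10 sites, five regions or seven age groups are represented, although assumed prevalence runs from 5% to 37% across the age groups and kappa depends on prevalence.

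Meanwhile the design produces a much larger body of paired readings. What is at stake is the precision and coverage of the reported reliability, not the prevalence estimate.

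**Working it through.** **Inputs from the documents.** Table 8.3.1 gives group sizes 44, 81, 100, 90, 80, 70 and 53, with assumed prevalences of 5, 7, 12, 16, 20, 23 and 37%. Section 8.3 gives 5% withdrawal for radiographs, 545 women per region and about 2,700 in total. Section 6.1.2.3 specifies two radiographs per woman. Section 4 cites inter-observer kappa of 0.65 to 0.74 from the literature.

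**Assumptions, not in the documents.** The first 100 follow the planned age mix; one film set is one woman; the rating is fracture yes/no per woman; both readers call fractures at the same rate.

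**The plan's own figure.** The group sizes sum to 518. 518/0.95 = 545.3 (stated: 545), and 5 × 545 = 2,725 (stated: about 2,700). It reproduces.

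**Expected fractures.** (2.2 + 5.67 + 12 + 14.4 + 16 + 16.1 + 19.61)/518 = 85.98/518 = 16.6%, so about 17 per 100 women (binomial 95% range 10 to 24). The 15% cited in Section 1.1 would give 15. Women with both reads: 2,700 × 0.95 = 2,565, with about 426 fractures.

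**Model.** With prevalence p and kappa κ, the probability that both readers say fracture is p² + κp(1−p). Each discordant cell has probability (1−κ)p(1−p), and both say no fracture with probability (1−p)² + κp(1−p). At p = 0.166 and κ = 0.70 these are 0.124, 0.042 (twice) and 0.792.

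**Large-sample variance.** Var(κ) = [(1−κ)/n] × [(1−κ)(1−2κ) + κ(2−κ)/(2p(1−p))]. At κ = 0.70 and n = 100: 0.003 × (−0.12 + 0.91/0.2769) = 0.0095, so SE ≈ 0.097. At n = 2,565 the SE is 0.097/√25.65 ≈ 0.019.

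**Simulation of the 2×2 table (200,000 draws).** This picks up the skewness at n = 100.

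| True κ | 95% range, n = 100 | Chance observed κ ≥ 0.81, n = 100 | 95% range, n = 2,565 |
|---|---|---|---|
| 0.65 | 0.42–0.83 | 5% | 0.61–0.69 |
| 0.70 | 0.48–0.87 | 12% | 0.66–0.74 |
| 0.74 | 0.53–0.90 | 22% | 0.70–0.78 |
| 0.81 | 0.63–0.95 | 51% | 0.78–0.84 |

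With 2,565 women, readers with a true kappa of 0.74 would essentially never reach 0.81.

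**If a film is a single radiograph.** 100 films are then about 50 women, with about 8 fractured. The range at κ = 0.70 becomes 0.36–0.94, and readers at 0.74 reach 0.81 about 30% of the time.

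**Sensitivity to prevalence.** At κ = 0.74 and n = 100, the SE is 0.115, 0.092 and 0.085 for prevalences of 10%, 16.6% and 20%. The conclusion does not depend on the exact mix.

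**Subgroups.** At κ = 0.70, a region of 2,565/5 = 513 women has a half-width of 1.96 × 0.097/√5.13 ≈ 0.08. One of ten sites (about 257 women) has 1.96 × 0.097/√2.57 ≈ 0.12. These are good enough for description only.

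**The case against.** The first-100 test is a check on the readers before adjudication. Early timing is its purpose, so a complaint that it comes too soon would miss the point. That stands, and the check should stay.

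Four stronger readings are tempting, and the documents do not support them.

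- *The prevalence estimates are compromised.* They are not. Cases rest on the agreed or third-party result, and kappa enters no estimate, interval or case rule.
- *The study may pass or fail a 0.81 threshold by chance.* The value is only a descriptive label and triggers nothing. Nor are 100 films uninformative: readers at a true 0.65 would reach it only about 5% of the time. The weakness is mainly near 0.74.
- *The plan expects its own readers to fall at 0.65 to 0.74.* Section 4 attributes that range to differences in experience and method. The study uses two experienced, additionally trained radiologists and one method. The range is a useful yardstick, not a forecast.
- *The intra-observer re-reads should also be redrawn across sites.* That would either add reads or give up the timing before adjudication, so it is not free. The double reads supply inter-observer agreement only.

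Site coverage is also partly protected: the blinded readers are the same two for the study, technique is standardised, and every site submits sample radiographs for quality assessment beforehand. Film quality and case mix can still vary by site. Finally, Section 8.1 announces a separate SAP, which may add this analysis. The statement that it is not planned applies only to the text supplied.

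**Conclusion.** The point holds as a free improvement to a reported reliability figure. Under the stated assumptions, the planned sample gives a 95% range for kappa of about 0.48 to 0.87 at a true value of 0.70, or about 0.36 to 0.94 if a film is a single radiograph. It also need not represent all sites or regions. The paired readings that the design already generates would narrow this to about 0.66 to 0.74 and cover the whole study.

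The sizes depend on the per-woman yes/no rating and the Table 8.3.1 age mix. A per-vertebra or weighted analysis would have different precision. The recommendation does not depend on the exact figures, because the full set has about 25 times as many women (2,565/100 = 25.7). The gain is a precise and representative statement of how reproducible the primary endpoint is; the primary result does not change.

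**What to change.** Keep the first-100 intra- and inter-observer check as Sections 4 and 6.1.2.3 describe it, and state whether the 100 are women or single radiographs. Add to Section 8.1.1, or to the separate SAP before database lock:

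- inter-observer kappa with a 95% confidence interval from all double-read women, for any fracture (grade 1 to 3) per woman;
- weighted kappa for Genant grade, with the unit and weights stated;
- both overall, and descriptively by region or site.

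Use each reader's initial grade, recorded before any third-party review. The agreement rule already requires both grades to be known, so the only practical requirement is that they are kept in the database and not overwritten by the final decision. No additional reads or films are needed, the prevalence analyses stay as they are, and the cost is a few lines of programming and one table.

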8.3 Sample Size and Power Calculations

The sample size of the study was calculated based on prevalence data per age group several large epidemiological studies [29-32, 36]. As the prevalence of vertebral fractures increases with age, the sample size will be determined as per age group by setting a lower limit for each assumed age-based prevalence rate (Table 8.3.1), using Clopper-Pearson exact method [52] to compute the lower bound of the corresponding 95% CI at a 5% precision. A sample size of 545 at each geographic region will be statistically sufficient to cover all age groups in detecting the prevalence of vertebral fractures, assuming a 5% withdrawal rate for the spinal radiographs in the study. Considering geographic distribution (5 regions), a total sample size of approximately 2700 postmenopausal women aged 50 or above will be enrolled for the study. In addition, this sample size will yield a generally over 90% power at a 0.05 significance level to detect a geographic impact for the fracture prevalence by an odd ratio at 1.40 or 1.50, by using a univariate logistic model in estimating the change in probability.

Assuming a 40% nonresponse rate in population-based studies [56] and 5% ineligibility rate [32], invitation letters will be posted to approximately 4750 women in all regions.

Table 8.3.1 Sample Size Calculation by Age Group based Prevalence

Age group	Sample size	Assumed Prevalence	95% CI Lower Limit
50 - 54	44	5.0%	1.0%
55 - 59	81	7.0%	3.0%
60 - 64	100	12.0%	6.0%
65 - 69	90	16.0%	10.0%
70 - 74	80	20.0%	12.0%
75 - 79	70	23.0%	15.0%
>80	53	37.0%	26.0%

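### The plan gives a crude and an age-standardised overall fracture prevalence without saying which answers the primary objective; the crude rate reflects the age allocation, and the standardised rate has no suitable interval

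*Combined protocol and SAP*

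**What the plan says.** Section 8.1.1 sets the target: "The study's primary objective is to investigate the prevalence of radiographic vertebral fractures in community-dwelling postmenopausal women in China". There is no hypothesis test, so the prevalence estimate is the main result.

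The section describes two kinds of overall estimate. The first is unadjusted: "Point estimates (percentage) of prevalence by overall study population and by age group and/or geographic region will be calculated and displayed". The second is standardised: "Point estimates of prevalence rates by overall and geographic region will be adjusted by a nationwide age distribution using the database from Basic Statistics on" the 2010 national census, followed by "A direct method of adjusting rates will be made to give age-standardized prevalence". Table 8.1.1.1 then puts both in one row, "Overall Crude/Age-Standardized Rate Point and 95% CI", and treats the regional rows alike. Table 8.1.2.1 repeats the pattern for osteoporosis.

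On intervals, Section 8.1.1 says "This 95% CI is based on a direct calculation of the exact binomial distribution", with the Wilson score interval alongside. Footnote * to Table 8.1.1.1 applies these two methods to every row, including the standardised ones.

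On sampling, Section 3.2 says "a randomized stratified sampling will be performed by age group using a computerized random selection on various demographic records". Section 8.3 explains how the band sizes were reached: "the sample size will be determined as per age group by setting a lower limit for each assumed age-based prevalence rate".

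Section 8.1 announces a separate SAP. On standardisation, Section 8.1.1 defers to it only the optional use of regional age distributions, not the choice between crude and standardised.

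**The concern.** The objective asks for one number about women in China, and the plan supplies two that estimate different things. The standardised rate weights each age band by its share of the census population. The crude rate weights each band by the number of women enrolled in it, and those numbers were chosen to reach a lower confidence limit in each band.

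Vertebral fracture prevalence rises steeply with age, from 5% to 37% across the bands in Table 8.3.1. A sample with few women in their early fifties and many over 70 will therefore show a higher crude rate than a younger population would. A headline taken from the crude rate would misstate the national burden, and its confidence interval would give no warning of this. Without a designation, the choice of headline figure is still open once both are known.

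**Working it through.** **Inputs.** Band sizes per region, assumed prevalences and the 5% radiograph loss are from Section 8.3 and Table 8.3.1. The census age shares are not in the documents and are assumed below.

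**1. Reproduce the plan's sample size.** The seven band sizes sum to 44 + 81 + 100 + 90 + 80 + 70 + 53 = 518. Allowing for 5% loss, 518/0.95 = 545.3 (stated: 545). Five regions give 5 × 545 = 2725 (stated: approximately 2700). Evaluable women: 5 × 518 = 2590. The allocation in Table 8.3.1 is therefore the one behind the stated total.

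**2. Age mix of the planned sample.** Aged 50-54: 44/518 = 8.5%. Aged 70 or over: (80 + 70 + 53)/518 = 203/518 = 39%.

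**3. Expected crude rate**, Σnᵢpᵢ / Σnᵢ:

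(2.20 + 5.67 + 12.00 + 14.40 + 16.00 + 16.10 + 19.61)/518 = 85.98/518 = 16.6%.

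- Overall, n = 2590: exact 95% CI 15.2% to 18.1%. The Wilson interval agrees to within 0.05 point.
- One region, n = 518: exact 95% CI 13.5% to 20.1%.

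**4. Age-standardised rate**, Σwᵢpᵢ, from the same band prevalences and three assumed profiles (shares in %, youngest band first):

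| Assumed shares | Standardised rate | Crude minus standardised | Outside overall crude CI? | Outside one-region crude CI? |
|---|---|---|---|---|
| 25, 23, 17, 12, 10, 7, 6 | 12.7% | 3.9 points | yes | yes |
| 22, 21, 17, 13, 11, 8, 8 | 13.7% | 2.9 points | yes | no |
| 20, 19, 16, 14, 12, 10, 9 | 14.5% | 2.1 points | yes | no |

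For the first row: 1.25 + 1.61 + 2.04 + 1.92 + 2.00 + 1.61 + 2.22 = 12.65%.

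**5. Sensitivity to the assumed shares.** Equal shares in all seven bands give 17.1%, which is 0.5 point above the crude rate and inside its CI. A steeper decline (27, 24, 18, 12, 9, 6, 4) gives 11.8%, a gap of 4.8 points. The gap thus depends on how fast the shares fall with age. The overall crude CI excludes a standardised value once the gap reaches about 16.6 − 15.2 = 1.4 points.

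**6. A comparison from the documents.** Section 1.1 cites a prevalence of 15% in women aged 50 or older in China. That is 1.6 points below the expected crude rate and just outside its overall CI.

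**7. Sensitivity to clustering.** The planned binomial interval ignores the two-stage sampling. With an assumed design effect of 2, the overall crude lower limit falls to 14.6%, and the 14.5% profile is only just excluded. With 3 it falls to 14.2% and that profile is no longer excluded; the other two still are.

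**8. The interval for the standardised rate.** A directly standardised rate is a weighted sum of band proportions, not a single binomial count, so neither method in footnote * applies to it directly. A suitable standard error is √Σ[wᵢ²pᵢ(1 − pᵢ)/(5nᵢ)]. For assumed shares 22, 22, 18, 13, 10, 8, 7 the rate is 13.3%, with 95% CI 12.0% to 14.6%. Treating 13.3% as a binomial proportion on 2590 women gives 12.0% to 14.7%. The two are close here, so the present method is mis-specified for this rate but not shown to be badly wrong in size.

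**The case against.** The strongest reply is that the two rates do not have equal standing. Section 8.1.1 ties the unadjusted rate to the study population and says without condition that overall and regional rates will be adjusted to the national census. Since the objective concerns women in China, the adjusted rate is the natural reading. This stands: the population estimate is in the plan, and what is missing is a sentence naming it.

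A reader might infer that the sponsor could report whichever rate looks better. The documents do not support that. Both rates are prespecified with intervals, no test or threshold can be met by choosing between them, and dropping either would depart from the plan. Only the emphasis is open.

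A reader might also infer that regions will be compared on crude rates. Nothing says so. Regional rates are already to be standardised to one nationwide distribution, age-by-region rates are tabulated, and Section 8.1.2.2 lists both age and region for the regression models.

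Finally, the gap rests on assumed weights and on enrolment matching Table 8.3.1. Sampling is age-stratified, but no section sets a quota or cap by age band, and Section 6.1.1.1 describes letters sent in list order. This also stands. It limits the size that can be claimed, but not the point that no rate is designated.

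**Conclusion.** The point holds as a missing designation together with an unsuitable interval. It does not show that the plan lacks a population estimate. Section 8.1.1 favours the census-adjusted rate without naming it, and the crude rate, which follows a precision-based age allocation, should not be read as prevalence in women in China.

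The size is conditional. The 16.6% figure needs the Table 8.3.1 prevalences and an enrolment that follows its allocation. The gap of 2 to 4 points also needs census shares that decline with age at about the assumed pace. It would be wrong to read the crude interval as excluding the standardised rate in general: this applies to the overall rate with the planned binomial interval. It weakens under clustering and fails within a region for the two profiles with gaps of 2.1 and 2.9 points.

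The change should be made because it is cheap and settles the headline before the data are seen.

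**What to change.** In Section 8.1.1 and Table 8.1.1.1:

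- Name the age-standardised overall rate (2010 census, direct method) as the single primary estimate.
- State that any regional comparison uses the regional rates already standardised to that same nationwide distribution.
- Label crude overall and regional rates as descriptive of the enrolled sample and not a population estimate.
- Amend footnote * so that standardised rates take a CI from a stratum-weighted variance; keep the exact and Wilson intervals for crude rates.

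Make the same changes to Table 8.1.2.1 for osteoporosis.

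The cost is a few sentences, a footnote and a small change to the interval calculation, with no new data. Both rates are still reported. The headline figure is likely to be lower than the crude one.
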